5.4.3 Biomarker Analyses

The biomarker endpoints are:

- Change from baseline in tau PET signal
- Change from baseline in CSF biomarkers t-tau and p-tau
- Change from baseline in CSF amyloid biomarkers $A\beta(1-x)$, $A\beta(1-42)$, and $A\beta(1-40)$
- Change from baseline in plasma amyloid biomarker (eg, $A\beta(1-x)$)
- Change from baseline in plasma NFL and CSF NFL and Ng
- Change from baseline in volumetric MRI parameters (eg, total hippocampal volume etc.) at 24 months

Tau PET SUVR parameters (i.e., entorhinal cortex, parietal cortex, inferior temporal cortex, amygdala, hippocampus and parahippocampal cortex using inferior cerebellum cortex as reference region; left, right and bilateral) will be summarized as biomarker endpoints. vMRI parameters (i.e., total hippocampal volume, left hippocampal volume, right hippocampal volume, whole brain volume, total ventricular volume, cortical thickness – Mayo Index) will be summarized as biomarker endpoints.

The analysis of the above endpoints will be performed by using MMRM or ANCOVA model, without adjustment for multiplicity. For each endpoint, the treatment effect for elenbecestat 50 mg per day versus placebo will be tested at a significance level of 2-sided $\alpha = 0.05$. As tau PET and CSF biomarkers will be collected once within subject at different analysis visit, the ANCOVA model with factors of treatment group, visit, treatment group-by-visit interaction, randomization stratification variables (ie, region [7 levels], clinical disease staging [MCI due to AD, early stage of mild AD], and concurrent AD medication use at randomization (Visit 2) [yes, no]), *ApoE4* status, and baseline value as a covariate will be applied.

The relationship between clinical changes (CDR-SB, ADCOMS, ADAS-cog₁₁, ADAS-cog₁₄, MMSE, and FAQ) and changes in the biomarkers (amyloid PET, tau PET, plasma PD/biomarker, CSF biomarkers, vMRI) will be evaluated using correlation analysis. In the presence of strong or moderate correlation, a linear model will be fitted to further characterize the relationship between the changes in clinical endpoints and changes in biomarkers. For tau PET and CSF biomarkers, the clinical assessments close to assessment date in tau PET or CSF biomarkers will be used. The relationship between amyloid PET and tau PET and the relationship between CSF biomarkers and tau PET will be evaluated using the same analyses described above.

Only summary statistics will be provided for CSF $A\beta(1-x)$, CSF $A\beta(1-42)$, and CSF $A\beta(1-40)$ because of the limitation of available data for the analysis. If the available data for the analysis for the other CSF biomarkers and tau PET is not sufficient, the analyses for CSF biomarkers and tau PET endpoints may not be performed.

The relationship between exposure (in CSF, plasma) of elenbecestat with potential biomarkers of Alzheimer's disease as deemed appropriate will be evaluated graphically only if a trend in biomarkers with time of treatment is noted..

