3.1.3 Biomarker Objectives

- To determine whether elenbecestat is superior to placebo on brain tau pathology at 24 months as measured by tau PET in subjects with EAD
- To determine whether elenbecestat is superior to placebo on CSF t-tau and p-tau levels at 24 months in subjects with EAD
- To determine whether elenbecestat is superior to placebo on CSF A β levels at 24 months in subjects with EAD
- To determine whether elenbecestat is superior to placebo on plasma amyloid levels (eg, A β (1-x)) at 24 months in subjects with EAD
- To explore potential plasma and CSF biomarkers of AD (eg, neurofilament [NFL] and neurogranin [Ng])

- To evaluate the correlation between the effect of elenbecestat on brain tau pathology with the effect on CSF biomarkers of neurodegeneration at 24 months
- To determine whether elenbecestat is superior to placebo on hippocampal atrophy at 24 months in subjects with EAD as measured by changes in hippocampal volume using vMRI
- To evaluate whether elenbecestat is superior to placebo in preserving connectivity at 24 months in subjects with EAD as measured by task free fMRI
- To evaluate the correlation between the effect of elenbecestat on brain tau pathology with the effect on preserving connectivity (fMRI) at 24 months
- To explore the relationship between exposure (in CSF, plasma) of elenbecestat with potential biomarkers of Alzheimer's disease (AD), as deemed appropriate
- To explore the relationship between changes in brain amyloid levels (amyloid PET) and brain tau pathology (tau PET) at 24 months in subjects with EAD

If the data available for the analysis is not sufficient, the analyses for the following objectives may not be performed or modified to focus on other visit than 24 months.

- To determine whether elenbecestat is superior to placebo on brain tau pathology at 24 months as measured by tau PET in subjects with EAD
- To determine whether elenbecestat is superior to placebo on CSF t-tau and p-tau levels at 24 months in subjects with EAD
- To determine whether elenbecestat is superior to placebo on CSF A β levels at 24 months in subjects with EAD
- To evaluate the correlation between the effect of elenbecestat on brain tau pathology with the effect on CSF biomarkers of neurodegeneration at 24 months
- To explore the relationship between changes in brain amyloid levels (amyloid PET) and brain tau pathology (tau PET) at 24 months in subjects with EAD

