7 CHANGES IN THE PLANNED ANALYSES

The following analyses will be added because they were focused on DSMB analyses.

- ADAS-cog₁₁
- TEAE by SOC/PT based on FDA-defined cognitive PTs
- Abnormal body weight change
- Summary of ADAS-cog RCI Alert Triggered by visit
- Subgroup analysis for very mild subjects defined as baseline CDR-SB \leq 1.5 and baseline MMSE \geq 27

The definition of time to worsening of CDR score by 24 months will be modified to use the date of second worsening instead of the date of first worsening in order to focus on sustained worsening.

The analyses to evaluate change from last dose will be added in CDR-SB, ADCOMS, ADAS-cog₁₁, ADAS-cog₁₄, MMSE, and ADAS-cog₁₄ Word List (immediate recall and delayed recall) instead of the analysis for 27 month in CDR-SB.

The following analyses will be conducted as one of sensitivity analyses instead of MMRM by censoring the data after change in concomitant AD medications to minimize the impact not only change in concomitant AD medications but also treatment discontinuation.

- MMRM by censoring the data after intercurrent events (i.e., treatment discontinuation or change in concomitant AD medications)

Several analyses for TEAEs relating to abnormal dreams, nightmares, or sleep terror and TEAEs of clinical interest will be added to evaluate safety profile more.

The following analyses will be removed from the planned analyses because there is a smaller sample size than originally planned.

- Analysis for amyloid PET SUVR, other biomarker endpoints, and exploratory endpoints by study level
- Analysis for CSF A β (1-x), CSF A β (1-42), and CSF A β (1-40) except summary statistics
- Statistical analysis for EQ-5D, QoL-AD, and Zarit's Burden Interview to compare elenbecestat 50 mg versus placebo
- Analysis for OLE data except specified in this SAP

The analyses for tau PET and CSF will be modified to include the assessments collected at early discontinuation visit as much as possible.

The following analyses will be reported separately from the CSR.

- Analysis for functional magnetic resonance imaging (fMRI)

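### Correlations involving tau PET and CSF tau, NFL and neurogranin have no elapsed-time term, although each subject is measured once and at differing visits

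*SAP*

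**What the plan says.** Section 3.1.3 frames the biomarker relationships at one common time, for example "To evaluate the correlation between the effect of elenbecestat on brain tau pathology with the effect on CSF biomarkers of neurodegeneration at 24 months". Section 3.1.2 lists the relationship between clinical and biomarker changes at 24 months as a secondary objective.

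Early termination broke that common time. Section 7 states: "The analyses for tau PET and CSF will be modified to include the assessments collected at early discontinuation visit as much as possible". Section 8.2 sets no limit after last dose for tau PET or for CSF total tau, p-tau, NFL and neurogranin.

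Section 5.4.3 recognises the consequence for the treatment comparison: "As tau PET and CSF biomarkers will be collected once within subject at different analysis visit, the ANCOVA model with factors of treatment group, visit" and treatment-by-visit interaction, among other terms. The next paragraph turns to relationships. Clinical changes and "changes in the biomarkers (amyloid PET, tau PET, plasma PD/biomarker, CSF biomarkers, vMRI) will be evaluated using correlation analysis". Then: "In the presence of strong or moderate correlation, a linear model will be fitted to further characterize the relationship". On timing, the only instruction is "For tau PET and CSF biomarkers, the clinical assessments close to assessment date in tau PET or CSF biomarkers will be used". For marker against marker, "the relationship between CSF biomarkers and tau PET will be evaluated using the same analyses described above", and tau PET against amyloid PET is handled in the same way. No visit, elapsed-time or treatment term is named for the correlation or the linear model.

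The same section limits CSF Aβ(1-x), Aβ(1-42) and Aβ(1-40) to summary statistics. The point therefore concerns tau PET and CSF t-tau, p-tau, NFL and neurogranin.

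**The concern.** The disease is progressive, so on average a subject assessed late shows more change from baseline than one assessed early, on the clinical scale and on any marker that tracks progression. Choosing the clinical score nearest the scan or lumbar puncture aligns the two measurements with each other. It does not remove time, because both changes then carry the same elapsed time. In a correlation pooled over subjects with different follow-up, part of the association is simply length of follow-up, even if the two changes are unrelated at any fixed time. This would arise within the placebo arm alone, so adjusting for treatment group would not cure it.

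At stake are the secondary objective linking clinical and biomarker change and the marker-to-marker objectives. Their results could be read as evidence that a marker tracks decline when some of the association reflects when subjects were measured.

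**Working it through.** **Inputs from the SAP.** Placebo CDR-SB change at 24 months: mean 1.46, SD 2.05, with a 25% reduction, 30% dropout, 90% power and two-sided 0.05 (Section 4). The mean/SD ratio is 1.46/2.05 = 0.71. One measurement per subject at differing visits (5.4.3) is read here as one post-baseline value.

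**Check of those inputs.** The SAP gives no figure for the correlation analysis, so its sample size is reproduced instead. The difference is 0.25 × 1.46 = 0.365, and n = 2(1.96 + 1.2816)² × 2.05² / 0.365² = 663 per arm. Then 663/0.70 gives 948 per arm, or 1,896 in total, against 1,900 stated.

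**Assumptions not in the SAP.** The distribution of assessment times; linear mean progression, the same for all subjects; the biomarker's 24-month mean change in SD units (k); and how residual spread grows with time.

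**Formula.** If changes X and Y are independent given time T, then r(X,Y) = r(T,X) × r(T,Y). With T as a fraction of 24 months, r(T,X)² = k²Var(T) / [k²Var(T) + V]. V is the mean residual variance relative to its 24-month value.

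**Worked case.** Times 6, 12, 18 and 24 months equally often, variance proportional to time: Var(T) = 0.078125, V = 0.625.
- Biomarker with k = 2: r² = 0.3125/(0.3125 + 0.625) = 0.333. Two such biomarkers therefore correlate at 0.33.
- CDR-SB with k = 0.71: r² = 0.0396/0.6646 = 0.0596, so r = 0.244. Against that biomarker, 0.244 × 0.577 = 0.14.

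**Range for CDR-SB against a biomarker.** Times spread evenly over months 3 to 24, with no association at any fixed time. The percentage is the simulated chance of p < 0.05 at an assumed n = 150 (4,000 replicates).

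| Residual spread | k = 0.71 | k = 1.5 | k = 3 |
|---|---|---|---|
| Constant SD | 0.04 (7%) | 0.08 (16%) | 0.13 (35%) |
| Variance proportional to time | 0.07 (17%) | 0.13 (37%) | 0.20 (70%) |
| SD proportional to time | 0.10 (27%) | 0.17 (56%) | 0.25 (84%) |

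Other timings, same three ratios: months 12 to 24 only, 0.02 to 0.09; all at 24 months, 0. A deliberately extreme split, half at 6 and half at 24 months, gives 0.07 to 0.29.

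**Range for biomarker against biomarker (equal k).** Months 6 to 24 with variance proportional to time: 0.03 (k = 0.5) to 0.33 (k = 2). Months 3 to 24 on the same basis: 0.37 at k = 2. Months 3 to 24 with constant SD: 0.04, 0.16 and 0.42 at k = 0.71, 1.5 and 3. These are scenarios, not bounds. Tighter timing lowers them, and a large k combined with fast-growing spread raises them.

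**After adjustment for T.** The mean partial correlation is about 0.00 in every months 3 to 24 scenario simulated for CDR-SB. The false-positive rate is about 5% with constant SD, 7% to 9% with variance proportional to time, and 12% to 14% with SD proportional to time.

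**The case against.** The strongest reply is that the SAP is silent rather than wrong. It never says the correlation is unadjusted or pooled over visits, it does not list the linear model's covariates, and Sections 9 and 11 leave derivations and layouts to other documents. Sections 3.1.3 and 5.1.3 allow these analyses to move to visits other than 24 months, and a visit-by-visit correlation would largely remove the problem. This stands in part: a reader might infer that pooling is specified, and it is not. But the date-matching rule is most naturally read as pooling, and a programmer following 5.4.3, which lists terms for the adjacent ANCOVA, would run a plain correlation.

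A reader might also infer that elapsed time would by itself carry clinical correlations over the strong-or-moderate threshold. The documents do not support that. The SAP gives no cut-off, and the mean induced value with CDR-SB stays below 0.3, taken here as an assumed mark for moderate. At n = 150 the simulated chance of an absolute correlation of 0.3 or more is 11% or less except in the most extreme cell of the table (about 30%). At n = 50 it runs from 4% to 40%, part of which is sampling noise.

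The size also depends on the assumptions. The 0.33 between biomarkers needs both to shift by 2 SD on average over 24 months. About half the subjects receive elenbecestat. If it changes a marker's time course, neither the size nor the direction of the bias follows from these calculations.

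Finally, the analyses lie outside the testing hierarchy (5.3.3), and the tau PET and CSF analyses may be dropped for lack of data (5.4.3). That limits the consequence. It does not make the method sound if they are run.

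**Conclusion.** The point holds as a weakness of the specified method. Section 5.4.3 handles differing assessment times in the treatment model for these markers and omits them in the relationship analyses that follow. Taken as written and pooled over visits, shared elapsed time adds a spurious correlation of about 0.02 to 0.25 with CDR-SB change, which is small to modest. Between two biomarkers it is about 0.03 to 0.4, which can be material. Only the CDR-SB ratio comes from the SAP; the other inputs are assumed.

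The point covers tau PET and CSF t-tau, p-tau, NFL and neurogranin. Extending it to all CSF markers would be wrong, since the amyloid species are not correlated with anything under this plan. Nor does it bear on the primary or key secondary results, none of which uses these correlations.

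**What to change.** In 5.4.3, state that correlations involving tau PET or CSF t-tau, p-tau, NFL and neurogranin are partial correlations adjusted for time from first dose to the biomarker assessment, as a continuous variable. An alternative is to correlate residuals from a model containing analysis visit, which matches the ANCOVA already specified. Put the same time or visit term in the follow-on linear model.

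Add variance-robust inference. A time covariate alone removes the bias in the mean correlation but leaves a false-positive rate of 7% to 14% if spread grows with time. If visit-specific correlations were intended, say so.

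The cost is one degree of freedom per correlation for continuous time (more for visit as a factor), a few sentences in the SAP and slightly more programming. The assessment dates are already collected, and the slope model in 5.4.2 already uses continuous assessment time.

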5.4.4 Exploratory Analyses

The exploratory endpoints are:

- Time to change of concomitant AD treatment (ie, dose increase and/or initiation of treatment with AChEI or memantine after randomization) by 24 months
- The proportion of subjects at 24 months who received dose increases and/or initiation of treatment with AChEI or memantine after randomization
- The rate of change over time (mean slope) based on NPI-10 item score over 24 months
- Change from baseline in NPI-10 item at 24 months
- Change from baseline in EQ-5D (subject self-reported, study partner self-reported, and subject measured by proxy) and QOL-AD (subject and study partner) at 24 months
- Change from baseline in Zarit's Burden Interview at 24 months

Time to change of concomitant AD treatment will be analyzed similarly as that used for the time to conversion to dementia based on clinical diagnosis, as described in the 2nd endpoints. Time to change of concomitant AD treatment is defined as time from randomization to the first dose increase and/or initiation of treatment with AChEI or memantine after randomization. If randomization date is not same as the first dose date, the first dose date will be used instead of randomization date. For subjects without any change of concomitant AD treatment by the end of study, the time to change of concomitant AD treatment will be censored at the date of 24 month visit (for completers) or the date of study discontinuation (for dropouts). For subjects with dose decrease or dose stop of treatment before dose increase and/or initiation of treatment, the time to change of concomitant AD treatment will be censored at the dose decrease or dose stop date.

The proportion of subjects with any change of concomitant AD treatment at 24 months will be analyzed similarly as that used for the proportion of subjects with dementia diagnosis at 24 months, as described in [section 5.4.2](#).

The rate of change over time (mean slope) based on change from baseline in the NPI-10 item will be analyzed in a manner similar as that used for the rate of change over time (mean slope) for the change from baseline in CDR-SB, as described in [section 5.4.2](#).

Analysis of the change from baseline exploratory endpoints will be performed to compare elenbecestat versus placebo by using MMRM or ANCOVA model. For each of them, the treatment effect of elenbecestat 50 mg per day versus placebo will be tested at a significance level of 2-sided alpha = 0.05. These endpoints include:

- Change from baseline in NPI-10 item at 24 months

The following endpoints will be summarized by treatment group.

- Change from baseline in EQ-5D (subject self-reported, study partner self-reported, and subject measured by proxy) and QOL-AD (subject and study partner) at 24 months
- Change from baseline in Zarit's Burden Interview at 24 months

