The maximum estimated duration for each subject in the Core Study is approximately 29 months (ie, 2 months Prerandomization Phase, followed by 24 months of blinded treatment period and a 3 month follow-up period in the Randomization Phase).

[figure not shown]
The Core Study will consist of Prerandomization and Randomization Phases. The Prerandomization Phase starts with consent and ends with randomization, and has a duration of up to 50 days (plus an additional window of up to 30 days if required). Subjects who participate in the optional longitudinal tau PET substudy will be permitted an additional window of up to 5 days (resulting in a total of up to 85 days) in order to accommodate the additional tau PET scan required to be performed during prerandomization. Screening assessments/procedures have been organized into 5 distinct tiers. All assessments and procedures in each tier should be completed, and eligibility to continue confirmed, before any assessments/procedures from the next tier commence. All Screening Visit assessments must be completed in the tiers as instructed, and eligibility to continue in the study confirmed, before any Visit 2 assessments commence. All subjects will be assessed for eligibility using cognitive assessments to confirm that subjects meet the diagnostic criteria for EAD including MCI due to AD and the early stages of mild AD, and that they do not have other medical conditions that may interfere with study participation. The diagnosis and clinical disease staging will be verified via a central review process and adjudicated if necessary (adjudication will only occur when there is a discrepancy between the diagnosis and clinical disease staging made by the site compared to that determined by the central review process; moreover, where adjudication is required, it will be undertaken by an independent assessor(s)).

The Randomization Phase consists of a Treatment Period and a Follow-Up Period. The Treatment Period will last 24 months. Subjects will be randomized at Visit 2 (Day 1) to receive elenbecestat 50 mg per day or placebo administered orally, once daily (QD) in the morning with or without food. The Follow-up Period will last for 12 weeks and is required for all subjects, regardless of whether they completed all 24 months of treatment or discontinued study drug early.

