All subjects who discontinue study drug before reaching 12 months of treatment during the Core Study will also be asked to return to the clinic for a 12 month clinical assessment and then again at 24 months. Subjects who discontinued study drug between 12 and 24 months of treatment will be asked to return to the clinic for a 24 month clinical assessment.

Eligible subjects may enter the Extension Phase immediately following the completion of Visit 15 (final follow-up visit) of the Core Study. Subjects who are eligible to participate in the Extension Phase but who do not transition to the Extension Phase on the day of Visit 15 may enter the Extension Phase any time within 4 weeks of Visit 15. All subjects who enter the

Extension Phase will be treated with elenbecestat, including the subjects who received placebo during the Core Study. For all subjects, assessments performed at Visit 15 will serve as baseline values for the Extension Phase.

Figure 1 Study Design of E2609-G000-301/302

Elenbecestat = Test drug, PET = positron emission tomography, R = randomization.

- a: Subjects who participate in the optional longitudinal tau PET substudy will be permitted an additional window of up to 5 days (resulting in a total of up to 85 days) in order to accommodate the additional tau PET scan required to be performed during prerandomization. (revised per Amendment 05)
- b: The last day of the Core Study (Visit 15) is also the first day of the Extension Phase

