5.2.5 Prior and Concomitant Therapy

All investigator terms for medications recorded in the eCRF will be coded to an 11-digit code using the World Health Organization Drug Dictionary (WHO DD). The number (percentage) of subjects who took prior, concomitant, current and treatment-emergent concomitant medications will be summarized on the Safety Analysis Set by treatment group, Anatomical Therapeutic Chemical class, and WHO DD preferred term (PT). Prior medications will be defined as medications that stopped before the first dose of study drug. Concomitant medications will be defined as medications that (1) started before the first dose of study drug and were continuing at the time of the first dose of study drug, or (2) started on or after the date of the first dose of study drug up to the date of the last dose. Current medication will be defined as medications that started before the first dose of study drug and were continuing at the time of the first dose of study drug. Treatment-emergent concomitant medication will be defined as medications that started on or after the date of the first dose of study drug up to the date of the last dose. All medications will be presented in subject data listings. Medications taken during the 12-week Follow-Up Period will also be recorded.

Prior and concomitant therapies for AD will be summarized separately.

Subjects' status on AD medications will be summarized by overall and each clinical disease staging.

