5.4.4 Exploratory Endpoints

The exploratory endpoints are:

- Time to change of concomitant AD treatment (ie, dose increase and/or initiation of treatment with AChEI or memantine after randomization) by 24 months
- The proportion of subjects at 24 months who received dose increases and/or initiation of treatment with AChEI or memantine after randomization
- The rate of change over time (mean slope) based on NPI-10 item score over 24 months
- Change from baseline in NPI-10 item at 24 months
- Change from baseline in EQ-5D (subject self-reported, study partner self-reported, and subject measured by proxy) and QOL-AD (subject and study partner) at 24 months
- Change from baseline in Zarit's Burden Interview at 24 months

Time to change of concomitant AD treatment will be analyzed similarly as that used for the time to conversion to dementia based on clinical diagnosis, as described in the 2nd endpoints. Time to change of concomitant AD treatment is defined as time from randomization to the first dose increase and/or initiation of treatment with AChEI or memantine after randomization. For subjects without any change of concomitant AD treatment by the end of study, the time to change of concomitant AD treatment will be censored at the date of last assessment of concomitant medication.

The proportion of subjects with any change of concomitant AD treatment at 24 months will be analyzed similarly as that used for the proportion of subjects with dementia diagnosis at 24 months, as described in section 6.4.2.

The rate of change over time (mean slope) based on change from baseline in the NPI-10 item will be analyzed in a manner similar as that used for the rate of change over time (mean slope) for the change from baseline in CDR-SB, as described in section 6.4.2.

Analysis of the change from baseline exploratory endpoints will be performed to compare elenbecestat (E2609) versus placebo by using MMRM or ANCOVA model. For each of them, the treatment effect of elenbecestat (E2609) 50 mg per day versus placebo will be tested at a significance level of 2-sided $\alpha = 0.05$. These endpoints include:

- Change from baseline in NPI-10 item at 24 months
- Change from baseline in EQ-5D (subject self-reported, study partner self-reported, and subject measured by proxy) and QOL-AD (subject and study partner) at 24 months
- Change from baseline in Zarit's Burden Interview at 24 months

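### Time to change of AD treatment is censored at a study-status date, not at the last date on which AD medication was reviewed; the rule changed from SAP v1.0 and Section 7 does not list the change

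*SAP*

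**What the plan says.** Section 5.4.4 of SAP v2.0 defines the endpoint as "time from randomization to the first dose increase and/or initiation of treatment with AChEI or memantine after randomization". It is to be analysed like time to conversion to dementia (Cox model, with a Kaplan-Meier 24-month proportion). For subjects without an event, the time "will be censored at the date of 24 month visit (for completers) or the date of study discontinuation (for dropouts").

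On medication recording, Section 5.2.5 classes a medication as treatment-emergent if it "started on or after the date of the first dose of study drug up to the date of the last dose", and adds: "Medications taken during the 12-week Follow-Up Period will also be recorded." It describes no later recording, but it does not say that recording ends there.

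On time in the study, Section 3.2 states: "The Follow-up Period will last for 12 weeks and is required for all subjects". Subjects who stop drug before 12 months "will also be asked to return to the clinic for a 12 month clinical assessment and then again at 24 months". For later stops: "Subjects who discontinued study drug between 12 and 24 months of treatment will be asked to return to the clinic", in their case for a 24-month assessment. Section 3.2 does not say whether medication is reviewed at these returns.

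In Section 5.4.4 of both v1.0 SAPs (301 and 302), the time for event-free subjects "will be censored at the date of last assessment of concomitant medication". Section 7 of v2.0 does not mention that this rule was replaced.

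**The concern.** In a time-to-event analysis a subject should stay in the risk set only while the event could be seen. The 24-month visit and the study-discontinuation date describe study status. Either can fall after the last occasion on which anyone asked about AChEI or memantine use. When it does, the interval between counts as time without a change, although a change in it could not have been recorded.

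Two groups are exposed:

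- Subjects lost to follow-up or withdrawing consent (both listed as reasons for leaving in Section 5.2.2), if the recorded discontinuation date is later than the last medication review.
- Subjects who stop drug early, stay in the study beyond the 12-week follow-up, and are not asked about medication at the month-12 or month-24 return.

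The result would be too low an event rate and too low a 24-month proportion. The shortfall grows with the share of drug stoppers, so unequal stopping would make the arm with more stops look as if it needed fewer AD drugs. If that arm were elenbecestat, the error would favour the hypothesis that this endpoint examines.

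**Working it through.** **Comparison within the document.** Section 5.4.2 of v2.0 censors time to CDR worsening at the last CDR assessment and time to dementia at the last diagnosis. The v1.0 rule for the present endpoint followed the same principle; the v2.0 rule does not. Section 7 does report a comparable change, from the first to the second worsening date for the CDR endpoint.

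**The plan's own figure.** The SAP gives no event rate, power or stop rate by arm for this endpoint, so there is nothing to reproduce. Its only attrition figure is the 30% dropout in Section 4. All rates below are assumptions.

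**Step 1: the largest possible gap.** Take described recording to end at last dose + 12 weeks (2.8 months) and suppose the subject stays to month 24. The gap is 24 − (month of last dose) − 2.8.

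| Last dose | Gap | Share of 24 months |
|---|---|---|
| Month 3 | 18.2 months | 76% |
| Month 6 | 15.2 months | 63% |
| Month 12 | 9.2 months | 38% |
| Month 21 or later | about 0 | about 0% |

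Subjects who complete treatment have no such gap, nor do stoppers who leave at or before the end of follow-up.

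**Step 2: effect on the 24-month proportion, with no drug effect.** Assume a constant hazard with a true 24-month proportion of 20%, so λ = −ln(0.80)/24 = 0.0093 per month and F(t) = 1 − exp(−λt). Assume stops uniform over months 1 to 20, all stoppers staying to month 24, and no recording after follow-up. With stop share p:

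reported proportion = (1 − p) × F(24) + p × average of F(min(24, s + 2.8))

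The average for stoppers is 11.5%.

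- p = 15%: 0.85 × 20% + 0.15 × 11.5% = 18.7%
- p = 35%: 0.65 × 20% + 0.35 × 11.5% = 17.0%
- Ratio of cumulative hazards: ln(1 − 0.170)/ln(1 − 0.187) = 0.90. A simulated Cox model gave 0.92.
- p = 20% versus 30%: about 0.95.

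**Step 3: simulation with other assumptions.** Here stops are uniform over 24 months and recording ends 3 months after last dose.

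- With 30% stopping and all staying, a true 20% is reported as 17.8% and a true 40% as 36.0%.
- With a true ratio of 1 and a true proportion of 30%, stops of 35% versus 25% give 0.95 if all stay and 0.98 if half stay.
- Stops of 40% versus 20% give 0.91 and 0.96.
- If no stopper stays on, there is no bias from this source.
- Censoring at the end of recording gives about 1.00 throughout.

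**Step 4: early termination.** Using the Step 2 model, let potential follow-up at termination be uniform from 4, 6 or 8 months up to 25 months, so that about 5 to 6% could reach month 24.

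| Stops | All stay | Half stay | None stay |
|---|---|---|---|
| 15% versus 35% | about 0.95 | 0.97 to 0.98 | about 1.00 |
| 20% versus 30% | about 0.97 | about 0.98 to 0.99 | about 1.00 |

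**The case against.** The strongest reply is that the unobserved time is inferred from silence. Section 5.2.5 adds follow-up medications to what is recorded and sets no end. Its last-dose limit defines a category for summary tables and is not a collection schedule. What is asked at the month-12 and month-24 returns would normally be in the protocol, which is not shown. If medication history is taken there, the time is observed and the rule does little harm to these subjects. The AD-medication flag in Section 8.4 carries forward to later visits but does not settle the question. This objection stands, and it makes the bias conditional.

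A reader might infer that recording stops 12 weeks after last dose, so that the event rate is definitely understated. The documents do not say so. A reader might also suppose that only changes up to last dose count, which would widen the bias. The event definition in Section 5.4.4 has no last-dose limit, so that reading fails too.

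The second reply also stands. SAP v2.0 was written after both studies were terminated early, so long stays after stopping drug were cut short and the Step 2 and 3 figures probably overstate the effect. Stop rates by arm appear nowhere in the document. The DSMB form of 11 September 2019 calls the adverse event profile on active drug worse than placebo, which makes unequal stopping plausible but does not measure it.

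Neither reply explains why the rule moved away from the last medication assessment, or why the change is unlisted.

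**Conclusion.** The point holds as a conditional one. What the text establishes is that v2.0 ends risk time at a study-status date, that this departs from v1.0 and from the parallel dementia endpoint, and that Section 7 is silent. Whether bias follows depends on whether AD medication was reviewed up to the censoring date.

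If it was not, a true ratio of 1 would appear as roughly 0.90 to 0.98 under the assumed unequal stop rates with half or all stoppers staying to month 24. Early termination probably brings it closer to 1: about 0.95 to 0.99 in the Step 4 cases with half or all staying. The direction favours whichever arm has more drug stops. If medication was reviewed throughout, the effect is close to nil.

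The endpoint is exploratory and tested without multiplicity adjustment. Primary and key secondary conclusions are not affected. The correction is worth making because it removes the bias if it exists and changes almost nothing if it does not.

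**What to change.** In Section 5.4.4, censor event-free subjects at the earlier of the currently stated date and the date of the last concomitant-medication assessment. Because v2.0 does not define that date, add a definition: the last visit or contact at which AD medication was reviewed. Use the same date for the Kaplan-Meier 24-month proportion, and list the change from v1.0 in Section 7. A sentence on whether medication is recorded at the month-12 and month-24 returns would let the reader judge whether any gap exists.

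The cost is SAP wording and one derived date. No new data are needed.
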